Based on pilot data and utilizing only the moderate to high risk group (>2 segments of Myostrain determined segments >17%), the outcome expected would be 12.8 +/- 4.7 dysfunctional segments for the intervention group and 16.8 +/- 7.8 dysfunctional segments for the control group (and using average of 4.7 and 7.8 for the standard deviation for the overall outcome) at 6 months. This same parameter will be followed at the other time points, including 1 year, 2 years, and 3 years, but the primary endpoint will be at 6 months. With these calculations, 102 patients are required to have a 90% chance of detecting, as significant at the 5% level, a decrease in the primary outcome measure from 16.8 in the control group to 12.8 in the experimental group (number of dysfunctional segments (>17%)).

The sensitivity, specificity, and diagnostic accuracy of each reader to detect changes in myocardial function will be determined for quantitative SENC-CMR. Cutoff-values used to calculate sensitivity and specificity of the quantitative SENC parameters were determined using data previously published. The cutoff for the % of MyoStrain segments <= -17% (based on 37 left ventricular segments) in detecting subclinical cardiotoxicity in the PREFECT50 planned interim analysis was 68% and the cutoff for detecting clinical cardiac dysfunction was 49%; a cutoff of 80% differentiates normal cardiac function from patients experiencing functional decline. McNemar's test with continuity correction will be used to compare the diagnostic performance of each of the SENC-CMR cutoff parameters. Additionally, Receiver Operating Characteristic curves as well as Precision Recall curves will be generated to calculate and compare the area under the curves to determine the diagnostic performance of changes in strain parameters and standard assessments. Inter- and intra-observer variability will also be determined for each of the above parameters using intraclass correlation.

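### Section 11 averages the two standard deviations rather than the variances: the planning SD should be 6.44, not 6.25, and 90% power needs about 110 patients, not 102

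*Combined protocol and SAP*

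**What the plan says.** The power paragraph of Section 11 (Statistical Considerations) takes its expected 6-month values from pilot data in moderate-to-high-risk patients: "12.8 +/- 4.7 dysfunctional segments for the intervention group" and "16.8 +/- 7.8 dysfunctional segments for the control group". It reduces the two SDs to one with the words "and using average of 4.7 and 7.8 for the standard deviation for the overall outcome". It concludes that "102 patients are required to have a 90% chance of detecting, as significant at the 5% level", a fall "from 16.8 in the control group to 12.8 in the experimental group".

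The section does not print the resulting SD, the formula, whether the test is one- or two-sided, or a dropout allowance. Section 5.7 gives 1:1 allocation and a current target of 40 evaluable patients, as do Sections 1.8 and 5.6 for the number. Section 11 still carries 102.

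**The concern.** The precision of a difference in means depends on the variances of the arms. With n patients in each arm, the variance of the difference is (SD₁² + SD₂²)/n, so the common SD that gives the same precision is the root mean square of the two SDs. The arithmetic mean of two unequal SDs is always smaller than that. The shortcut therefore always errs towards a smaller sample and a higher stated power.

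The consequence is that the sample size and power in Section 11 do not follow from the section's own means and SDs. This is a fault in an input, separate from the mismatch between 102 and 40 patients. If the power were restated for 40 patients with the averaged SD kept, the new figure would be too favourable as well.

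**Working it through.** **Inputs (Section 11 unless noted).** Means 12.8 and 16.8, so the difference is 4.0 segments. SDs 4.7 and 7.8. Significance level 5%, power 90%, stated total 102 (51 per arm). Allocation 1:1 (Section 5.7). Two-sided testing is an assumption, tested in step 2.

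**1. The two candidate SDs.**
- Mean of the SDs: (4.7 + 7.8)/2 = 6.25.
- Root of the mean variance: sqrt((22.09 + 60.84)/2) = sqrt(41.465) = 6.439.

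**2. Reproducing 102.** The normal formula is n per arm = 2(z₁₋α/₂ + z₁₋β)² SD²/d². With 1.960 and 1.2816, the factor 2(3.2416)² is 21.015.
- SD 6.25, two-sided: 21.015 × 39.0625/16 = 51.3 per arm, 102.6 in total. This matches the stated 102 if 51.3 is taken down to 51. Rounded up, it is 52 per arm, or 104.
- SD 6.25, one-sided: 41.8 per arm, rounded up to 42, or 84 in total. This does not match.
- SD 6.439, two-sided: 21.015 × 41.465/16 = 54.5 per arm, rounded up to 55, or 110 in total. This does not match.

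The stated figure therefore comes from the averaged SD and a two-sided test. The wording is not a loose description of a correct calculation.

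**3. Sample size for 90% power.**

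| Method | SD 6.25 | SD 6.44 |
|---|---|---|
| Normal, unrounded total | 102.6 | 108.9 |
| Normal, rounded up per arm | 104 | 110 |
| t-test (noncentral t) | 106 | 112 |
| Welch, using the two stated SDs | n/a | 112 |

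**4. Power at 51 per arm.** The normal formula is Φ(d/(SD·sqrt(2/n)) − 1.960).
- SD 6.25: 4/(6.25 × sqrt(2/51)) = 4/1.238 = 3.232, and Φ(1.272) = 89.8%. By t-test, 89.3%.
- SD 6.44: 4/(6.439 × sqrt(2/51)) = 4/1.275 = 3.137, and Φ(1.177) = 88.0%. By t-test, 87.4%. By Welch, 87.3%.

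**5. The current target, 20 per arm.**
- Power for 4.0 segments by t-test: 50.5% with SD 6.25, 48.2% with SD 6.44 (Welch 47.8%). By the normal formula: 52.5% and 50.2%.
- Difference detectable with 90% power by t-test: 6.6 segments with SD 6.25, 6.8 with SD 6.44.

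**The case against.** The algebra is not in dispute. The case on the other side concerns attribution, assumptions and weight.

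- **Not all of the gap comes from the SD.** Rounded up correctly, SD 6.25 already needs 104 (normal) or 106 (t). The SD alone moves these to 110 and 112, which is 6 patients in each case. In power it costs 1.8 points (normal) or 1.9 points (t). This stands. About 2 of the 8 patients between 102 and 110 are rounding.
- **Sidedness is not stated.** Section 11 says only "as significant at the 5% level" and speaks of a decrease. On a one-sided reading, 102 patients would give about 93% power even with SD 6.44. But a one-sided calculation yields 84, not 102, so two-sided is what the plan must have used. The assumption should be declared.
- **102 is no longer the target.** At 40 patients either SD gives roughly even odds of detecting the planned difference, so no enrolment decision turns on this. That is true, and the unexplained cut to 40 matters far more. But the 102-patient statement is current text, and the same SD would feed any replacement.
- **The inputs are uncertain.** The pilot in Section 2.3 has 15 subjects, 8 of them at moderate or high risk. If the SDs came from a group of that size (the source number is not given), an SD of 6.25 on 7 degrees of freedom has a 95% interval of about 4.1 to 12.7. A 3% correction is small beside that. It does not make the wrong average right.
- **The planned models may adjust for baseline.** With an assumed correlation of 0.3 between the baseline and 6-month counts (none is given), the residual SD would be 6.44 × sqrt(1 − 0.09) = 6.14, and power at 102 about 91% (normal). Section 11 makes no such allowance in its calculation, so this would be a different justification from the one stated.

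**Conclusion.** The concern holds. On Section 11's own means and SDs, the planning SD is 6.44, 90% power needs 110 patients (112 by t-test or Welch), and 102 patients give 87% to 88%. The effect is small: about 2 points of power and about 6 patients from the SD, with about 2 more from rounding down. The conclusion rests on a two-sided 5% test, an unadjusted comparison of 6-month means, equal arms and no dropout. The first is inferred from reproducing 102. The second and last reflect that the calculation mentions no adjustment or allowance. It does not put the trial's validity in question. It is a wrong input and a wrong power statement in current text, and worth correcting when Section 11 is brought into line with the 40-patient target.

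**What to change.** In Section 11, replace the averaged SD with 6.44, showing it as the square root of the mean of the two variances, and state that the test is two-sided. Say that 102 patients would give about 87% to 88% power and that 110 (normal) to 112 (t-test) would have been needed for 90%. Use 6.44 in whatever is stated for 40 evaluable patients: by t-test, about 48% power for 4.0 segments, or a detectable difference of about 6.8 segments at 90% power. If the sponsor wants to rely on baseline adjustment, give the assumed correlation and its source. The cost is a text change. The stated figures become slightly less favourable, and no extra patients are needed.

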1.5. Endpoints

The primary efficacy endpoint is the sensitivity and accuracy of detection of patients with myocardial dysfunction using MyoStrain® compared to standard assessments of cardiac function: left ventricular ejection fraction (LVEF), as well as end-systolic (LVESV), end-diastolic (LVEDV), and stroke (LVSV) volumes indexed to body surface area.

Changes in function based on clinical presentation, standard assessments, and all available metrics will be used to define the cardiotoxicity status of the patient. A clinical committee organized and chaired by the principal investigator will be used to classify each exam in both unblinded and blinded arms according to professional knowledge and derived from the ASE Expert Consensus Position Paper, the ESC Position Paper, and the ESMO Clinical Practice Guidelines. [1] [2] [3]

- Clinical cardiac dysfunction is defined as an absolute change in LVEF > 10% from baseline to below 53% combined with heart failure symptoms or abnormal cardiac biomarkers (troponin, BNP, or NT pro BNP).
- Subclinical CTX was defined as an asymptomatic patient with a greater than 15% decrease in LVEF that remains >= 53%, worsening GLS more than 15% from baseline, or abnormal cardiac biomarkers (troponin, BNP, or NT pro BNP).
- If no baseline information is available to compare metrics for categorizing cardiotoxicity status, considering most patients in the PROACT sub-study of the Survive Registry will have metastatic cancer with prior treatments including chemotherapy, physician discretion and patient presentation will provide the final decision on cardiotoxicity category. All available metrics will be used to classify patients at each assessment time point.

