1.8. Expected Duration

Based on an enrollment of 40 evaluable patients (a subset of the approximately 700 SURVIVE Registry patients enrolled annually across all SURVIVE participating sites) who demonstrate moderate to high risk of cardiotoxic effects during cardio-oncology treatment due to observed segmental dysfunction on baseline MyoStrain® evaluation, it is anticipated that all subjects will be enrolled within 12 months after study initiation. The study will end when the last enrolled subject completes the 36-month follow-up, data is analyzed and reports are written. Therefore, study duration is anticipated to be approximately 54 months.

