5.7. Sample size

40 evaluable patients will be randomized 1:1 to the MyoStrain® imaging guided arm versus the standard of care arm.

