importance of MyoStrain cardiac features compared to cardiac toxicity risk prediction based on standard assessment of variables LVEF, LVESV, LVEDV, and LV Stroke Volume Index (LVSVi). Endpoints will be evaluated based on discrete variables of MyoStrain values versus standard assessments. Considering many patients will have a complex management of cardioactive medications as well as cancer treatment regimen, the classification of cardiotoxicity status will be based on a clinical committee to designate whether the patient experienced no cardiotoxicity, functional decline without cardiotoxicity, subclinical cardiotoxicity, or clinical cardiac dysfunction at each exam timepoint. The last analysis will help to identify also any indication for interactions among variables studied. We will implement Intention-To-Treat-analysis, where the analyses of the two groups will be based on the initial treatment assignment in the two randomized groups. If in the follow-up data-points may be missing, we will check if the missing data-points are random and if several covariates can help in imputation of missing. We plan to use MI procedure of SAS Institute for such imputations. The regression will be implemented via GLM, LOGISTIC and MIXED (for statistical analysis of repeated measures) procedures in SAS. For mixed models, a comparison of models will be done via likelihood ratio test and by using the Akaike Information Criterion (AIC) and Schwartz's Bayesian Criterion (SBC). Graphical presentations will be implemented in R via LMER of LME4 mixed modelling build in functions, and specialized software GGPlot2 in R. Decision (known also as partition) trees will be implemented with SAS-Data Mining software. We will use also PYTHON-scikit machine learning package for testing the performance of partition-trees via random forest. A random forest is a meta estimator that fits a number of decision tree classifiers on various sub-samples of the dataset and use averaging to improve the predictive accuracy and control overfitting.

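### Sections 1.5 and 11 name different primary endpoints without ranking them, and the 90% power claimed for 102 patients is about 50% at the 40 now planned

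*Combined protocol and SAP*

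**What the plan says.** **Section 1.5 (Endpoints).** "The primary efficacy endpoint is the sensitivity and accuracy of detection of patients with myocardial dysfunction using MyoStrain", judged against LVEF and indexed left ventricular volumes. This compares tests within patients. A committee chaired by the principal investigator assigns a cardiotoxicity status at every exam.

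**Section 11 (Statistical Considerations), sizing paragraph.** The outcome is the number of dysfunctional segments, expected to be 16.8 (SD 7.8) in the control group and 12.8 (SD 4.7) in the intervention group. It is followed at other visits, "including 1 year, 2 years, and 3 years, but the primary endpoint will be at 6 months". The section prints the threshold as 17% without the minus sign; I read it as strain above -17%, as in Section 5.1. It then says "102 patients are required to have a 90% chance of detecting, as significant at the 5% level", and an earlier paragraph of the section also gives the number of subjects as 102.

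**Sample size elsewhere.** Section 5.7: "40 evaluable patients will be randomized 1:1 to the MyoStrain® imaging guided arm versus the standard of care arm". Section 1.8: "Based on an enrollment of 40 evaluable patients". Section 5.6 gives the same number.

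**Tests, all in Section 11.** "The regression will be implemented via GLM, LOGISTIC and MIXED (for statistical analysis of repeated measures) procedures in SAS". McNemar's "test with continuity correction will be used to compare the diagnostic performance of each of the SENC-CMR cutoff parameters". ROC and precision-recall curves are to be used to "compare the area under the curves to determine the diagnostic performance of changes in strain parameters and standard assessments".

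**The concern.** The two endpoints answer different questions. One asks whether MyoStrain classifies patients better than standard measures; the other asks whether giving physicians MyoStrain results changes the segment count. Either can succeed while the other fails. The three primary objectives in Sections 1.4 and 3 are also unranked, so they do not settle the matter. In an open-label trial, two different results could each be reported as the primary one, with no rule for choosing.

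The power statement matters separately. A reader who trusts 90% could take a null between-arm result as good evidence of no effect, when the trial had roughly an even chance of missing the planned difference.

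**Working it through.** **1. The two endpoints side by side**

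| | Section 1.5 | Section 11 |
|---|---|---|
| Quantity | Sensitivity and accuracy | Segments above -17% |
| Comparison | MyoStrain with standard measures, within patients | Guided with observational arm |
| Time | Every exam; none singled out | 6 months |
| Sample size | None | 102 |
| Test tied to it | None: McNemar is assigned to SENC cutoffs; ROC and precision-recall areas are compared with standard measures | None: GLM, LOGISTIC and MIXED are listed in general |

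**2. Reproducing 102**

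Inputs from Section 11: difference 16.8 - 12.8 = 4.0; SD (4.7 + 7.8)/2 = 6.25, the averaging the section describes; alpha 5%; power 90%.

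n per arm = 2 × [SD × (z_alpha + z_power) / difference]²

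Two-sided: 2 × [6.25 × (1.960 + 1.282) / 4.0]² = 51.3 per arm, or 102.6 in total. Rounded up per arm this is 104, within 2 patients of 102. With 51 per arm, power is 89.8% (normal approximation) or 89.3% (t test). A one-sided 5% test would need only 84, so 102 implies two-sided testing, although the plan does not state sidedness.

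**3. Power at the planned 40 (20 per arm)**

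Standard error = 6.25 × √(2/20) = 1.976, and 4.0/1.976 = 2.024. Normal approximation, two-sided: Φ(2.024 - 1.960) = Φ(0.064), about 52.5%. The t test uses the noncentral t distribution with 38 degrees of freedom. As a variant, the root-mean-square SD is √[(4.7² + 7.8²)/2] = 6.44.

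| SD | Two-sided, normal | Two-sided, t | One-sided, normal | One-sided, t |
|---|---|---|---|---|
| 6.25 | 52.5% | 50.5% | 64.8% | 63.4% |
| 6.44 | 50.2% | 48.2% | 62.5% | 61.2% |

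A simulated Welch test with the two separate SDs gives 47.7%, two-sided.

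**4. Difference detectable with 90% power at 20 per arm, two-sided**

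Normal approximation, SD 6.25: 6.25 × √(2/20) × (1.960 + 1.282) = 6.41 segments. The t test gives 6.57 (SD 6.25) and 6.77 (SD 6.44). The planned difference is 4.0.

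**5. Sensitivity to missing scans (assumed rates)**

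The plan does not define evaluable. If it does not already mean having a 6-month scan, 10% missing (18 per arm) gives 44-48% and 20% missing (16 per arm) gives 40-44%.

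**6. Precision of the Section 1.5 endpoint (illustration)**

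The plan gives no calculation to reproduce. If observed sensitivity were 80%, the exact 95% interval would be 56.3% to 94.3% with 20 reference-positive patients and 44.4% to 97.5% with 10. Both counts are assumptions.

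**The case against.** **Section 1.5 governs.** It is the formal endpoints section and matches the second primary objective, so the segment count could be read as a sizing device only. But Section 11 itself calls the count primary, and nothing subordinates it.

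**The reduction to 40 was deliberate.** It may have been, and a smaller trial can be legitimate. A reader might infer that 102 is an arithmetic error, or that the trial must return to 102. Neither is supported: the figure reproduces, and the fault is that Section 11 was not updated to match the rest of the current text.

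**One-sided testing or baseline adjustment restores the power.** One-sided power is at most 65%. Adjustment for baseline count multiplies the SD by √(1 - r²). The plan gives no correlation r. An assumed 0.5 yields 60-62%, and reaching 90% needs about 0.79-0.81.

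**The type I error is doubled.** A reader might infer this, but the plan states no rule allowing success on either endpoint. If it did, with 5% each, 1 - 0.95² = 9.75% would hold for two independent tests, and the general bound is 10%.

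**The choice can still be shown to be blind.** Section 11 releases the observational arm's full measures only at the end, and a reader might infer that a choice made before then is uninformed. That release date alone does not show it. Under Section 5.1 the vendor processes both arms' scans and knows the allocation. Under Section 1.5 the committee classifies exams in both arms. Under Section 10.1.3 the principal investigator reviews all patients' data at least every six months.

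**Conclusion.** The plan is wrong as written on this point and should be corrected. It has two unranked primary endpoints, neither with a test tied to it, and one lacks both an exam and a sample size. For the one that is sized, power for 4.0 segments at 40 patients is 48-53% two-sided, not 90%; the trial could detect about 6.4-6.8 segments with 90% power. These figures assume 20 per arm, no adjustment, all 40 measured at 6 months, and the plan's own means and SDs. The absence of a ranking was checked in the available text; Figures 2 and 5 and some pages were not available. The documents do not show that any result has been chosen selectively, only that nothing prevents it.

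**What to change.** 1. **Endpoint.** State the same primary endpoint in Sections 1.5 and 11, or an explicit hierarchy or alpha split. The 6-month segment count is the only candidate with a time point and a sample-size calculation; its drawback is that the vendor producing the values knows the allocation. If the diagnostic endpoint stays primary, give it one exam and a precision or power statement at 40.
2. **Power.** Replace the Section 11 claim with the power at 40, stating sidedness, SD and what evaluable means. Correct the other mention of 102 in that section.
3. **Test and population.** Tie one test to the primary endpoint, for example a GLM of the 6-month count on randomised arm adjusted for baseline count, analysed as randomised. Reconcile Section 6.2, which leaves subjects who withdraw consent out of the analysis as per protocol, with the intention-to-treat analysis and imputation in Section 11.
4. **Timing.** Date the choice and record who had already seen data by arm, including the vendor, the classification committee and the principal investigator.
5. **Diagnostic comparison.** Add a paired comparison of MyoStrain with one pre-stated standard-assessment rule. LVEF below 53% alone should not be set against subclinical status, because the LVEF branch of that definition requires LVEF of at least 53%; such patients could never be flagged. State how the committee reference overlaps with both tests: it uses LVEF, and it uses GLS, which the MyoStrain report also supplies.

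**Cost.** A text amendment and a dated record, with no new data. The stated power falls to about one half, and one stated primary endpoint may become secondary, which needs a documented reason.

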2.3. PROACT Pilot Clinical Testing

A single center, pilot study was performed to evaluate the ability of the MyoStrain® MRI software system to identify cardiotoxicity during cardio-oncology treatment of breast cancer and lymphoma patients. An interim analysis of 15 subjects from the PROACT Pilot study (VAL-1005P) is included below to provide additional clinical evidence that the MyoStrain® software is able to detect progression of myocardial dysfunction resulting from cardiotoxicity. The pilot study was performed by Principal Investigator Hr. Priv.-Doz. [name] (Facharzt für Innere Medizin, Kardiologie PD DR) at Marien Krankenhaus GmbH (Hamburg, Germany).

- **Patient Demographics**

Demographic	Average ± St Dev
Age (years)	52.2 ± 11.5
Body Surface Area (m ²)	1.8 ± 0.2
Body Mass Index (kg/m ²)	25.7 ± 4.7
History of Cancer (months)	1.4 ± 0.8
Charlson Comorbidity Index	1.4 ± 1.0

- **Baseline CMR Information**

Baseline CMR Information	Average ± St Dev
LVEF (%)	58.8 ± 5.3
LVEDV Index (ml/m ²)	77.6 ± 13.4
LVESV Index (ml/m ²)	32.1 ± 8.0
Stroke Volume Index (ml/m ²)	45.5 ± 7.8
T1 Value Pre-Contrast (msec)	1052.4 ± 44.6
T1 St Dev Pre-Contrast (msec)	52.4 ± 11.8
Global Longitudinal Strain (%)	-20.8 ± 1.9
Global Circumferential Strain (%)	-19.0 ± 1.8

# Segments > -10%	1.7 ± 1.5
# Segments > -17%	8.5 ± 4.7

- Baseline Risk Assessment of Developing Cardiotoxicity by Segmental MyoStrain®.** Patients were stratified as to their risk by the number of dysfunctional (> -10%) and abnormal segments (> -17%). These thresholds have been validated as previously described in Figure 1 above.

[figure not shown]
Cardiotoxicity Risk Level	Segmental MyoStrain® Criteria	Incidence
Low	≤ 1 Segment > -10% & < 9 Segments > -17%	46% (7/15)
Moderate	2-3 Segments > -10% or 9+ Segments > -17%	27% (4/15)
High	3+ Segments > -10% & 10+ Segments > -17%	27% (4/15)

- Baseline Echocardiography Data**

[figure not shown]
Baseline Echocardiography Data	Average \pm St Dev
LVEF (%)	63.9 ± 5.8
LVEDV Index (ml/m ²)	47.7 ± 10.1
LVESV Index (ml/m ²)	17.3 ± 6.4
Stroke Volume Index (ml/m ²)	30.3 ± 5.1
GLS (%)	-26.5 ± 14.6
E/E'	8.8 ± 2.0

Pts with Poor Acoustic Window: 4/14 (29%)

- Interim Results of Segmental Dysfunction and Global Measures Throughout Follow-up**

[figure not shown]

- Interim Results of Global Strain Evolution Throughout Follow-up

- Example of Low Risk Patient Not Experiencing Cardiotoxicity.

[figure not shown]

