11. STATISTICAL CONSIDERATIONS

The data of cardiac features measured will be stored in a WUSTL REDCap-supported database and transformed into a SAS, R, excel, and CSV dataset, so they can be analyzed by our team using SAS, R and PYTHON software packages.

At baseline and any other visit, the standard descriptive statistics will be used to summarize numeric variables, including the number of observed values, mean, standard deviation, median, minimum and maximum values. Summaries of categorical variables will include the number and percentage of observed values, at each level of the categorical variable. Baseline and demographic information will be summarized with standard descriptive statistics.

There will be more than 60 cardiac 3D features measured for each patient (subjects' n=102) resulting from use of MyoStrain SENC software, as shown in the schematic Figure 5. The results will be stratified based on the patient's segmental strain (longitudinal and circumferential) profile with -10% or -17% as the threshold to determine segmental dysfunction and the number of dysfunctional segments delineating patient risk. The patients will be selected at baseline for high cardiovascular risk, which will be important in cancer patients in responding to cardiotoxicity.

Patients will be separated by randomization into two groups. Those of whom the cardiac care will be served with prior knowledge of MyoStrain SENC data as measured in each visit, while the other half, with exception of 4 cardiac measures, they and their doctor will not have knowledge for the full cardiac features, but we will have access to these data also, only at the end of the study.

[figure not shown]

Figure 5: A schematic of measurements and statistical methods to be used for inferring for cardiotoxicity from results of baseline and also at 1, 3, 6, 12, 24 and 36 months' follow-up.

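### Section 11 still gives 102 patients and 90% power, but the trial is now set at 40 evaluable patients, for which the same inputs give about 50% power

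*Combined protocol and SAP*

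**What the plan says.** Three sections of the current text fix the size of the trial at 40. Section 5.7 states that "40 evaluable patients will be randomized 1:1 to the MyoStrain® imaging guided arm versus the standard of care arm". Section 1.8 opens with "Based on an enrollment of 40 evaluable patients", and Section 5.6 repeats it.

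Section 11 describes a different trial. It introduces the imaging features with "n=102) resulting from use of MyoStrain SENC software, as shown in the schematic Figure 5", and its power statement reads "102 patients are required to have a 90% chance of detecting, as significant at the 5% level, a decrease in the primary outcome measure". The inputs are "12.8 +/- 4.7 dysfunctional segments for the intervention group and 16.8 +/- 7.8 dysfunctional segments for the control group", combined by "using average of 4.7 and 7.8 for the standard deviation for the overall outcome". Section 11 places its primary endpoint for this count at 6 months.

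No section gives power, a detectable difference or expected precision for 40 patients, or a statistical reason for choosing 40.

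**The concern.** The conflict lies between operative sections of the current text. It is not a difference between the amendment log and the protocol. The log only suggests how it arose: the Version 6.0 changes replace 102 by 40 in Sections 1.8, 5.6 and 5.7 and list no change to Section 11.

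The 6-month segment count is the only comparison in the document that has a power calculation. It also bears on the third objective, the effect of MyoStrain® imaging on medical management. A reader who takes Section 11 at its word expects a true 4-segment difference to be missed one time in ten. If the real figure is about one in two, a non-significant result could be read as evidence of no effect when the trial could not have shown one reliably.

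**Working it through.** **Inputs**

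- Difference: 16.8 − 12.8 = 4.0 segments (Section 11).
- SD: (4.7 + 7.8)/2 = 6.25 (Section 11's own rule).
- Significance level 5% (Section 11). Sidedness is not stated.
- Current size: 40 evaluable, 1:1, so 20 per arm (Section 5.7).

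**Step 1. Reproduce the plan's figure.** Normal approximation, 90% power:

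n per arm = 2 (z₁₋α/₂ + z₀.₉₀)² (SD/difference)² = 2 (1.960 + 1.2816)² (6.25/4)² = 51.3, or 102.6 in total.

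This matches 102 to within rounding. One-sided 5% testing would give 41.8 per arm (84 in total after rounding up), so two-sided is the reading that fits. At 51 per arm the power is 89.8% (normal) or 89.3% (t-test).

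**Step 2. Power at 20 per arm, all else unchanged.**

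- Standard error = 6.25 × √(2/20) = 1.976.
- Normal approximation: Φ(4/1.976 − 1.960) = Φ(0.064) = 52.5%.
- Noncentral t, 38 degrees of freedom: 50.5%.

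The chance of missing the planned difference is therefore 47.5% to 49.5%.

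**Step 3. What 20 per arm can deliver.**

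- Difference detectable with 90% power: (1.960 + 1.2816) × 1.976 = 6.4 (normal), or 6.6 (t-test).
- Expected 95% CI half-width: 2.024 × 1.976 = 4.0 segments, against 2.5 at 51 per arm.

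**Step 4. Sensitivity to the SD** (20 per arm, difference 4, two-sided 5%).

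| SD assumption | Power (t-test) |
|---|---|
| 4.7 in both arms | 75% |
| 6.25 (the plan's value) | 50.5% |
| 6.44 = √((4.7² + 7.8²)/2) | 48% |
| 4.7 and 7.8 kept unequal (simulated, Welch) | 48% |
| 7.8 in both arms | 35% |

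Reaching 90% would need a common SD of 4 × 6.25/6.575 = 3.8, which is below both SDs that Section 11 gives.

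**The case against.** Four points deserve an answer.

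- **The sentence is conditional.** It says what 102 patients would achieve, not that 40 achieve 90%. That is true, and the defect is better called an inconsistency than a miscalculation. But Section 11 also gives 102 as the number of subjects, so it presents 102 as the design and leaves the real design without a power statement.
- **The calculation is only approximate.** Strictly, 51.3 rounds up to 52 per arm (104 in total), and averaging SDs rather than variances is slightly favourable. Both points stand, but they are small beside the fall from 90% to about 50%.
- **An adjusted analysis could do better.** Section 11 plans comparison with baseline and mixed models. The documents give no correlation between baseline and 6 months. As an illustration only, multiplying the SD by √(1 − r²) gives power of about 62% at an assumed r of 0.5 and 79% at 0.7. To reach 90%, r would have to be √(1 − (3.80/6.25)²) = 0.79. The figure of about 50% should therefore be labelled as unadjusted.
- **The inputs are fragile.** The only pilot shown is described as "An interim analysis of 15 subjects from the PROACT Pilot study (VAL-1005P". Section 11 uses only its moderate to high risk group, which by the Section 2.3 table would be 4 + 4 = 8 patients. This limits how precisely power can be stated for any sample size. It gives no support for 90% at 40.

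**Conclusion.** The concern holds. Section 11 states a sample size and power for a trial of 102, while the rest of the current text describes one of 40. On Section 11's own inputs, unadjusted power at 20 per arm is about 50%, against the 90% stated. The exact value depends on the SD (35% to 75% across the two SDs given), but neither of those SDs brings it to 90%.

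This rests on two-sided testing, which is inferred because it reproduces 102, and on reading 40 evaluable as 20 analysed per arm. The plan does not define evaluable. Fewer than 20 per arm with 6-month data would lower the power.

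The result concerns the 6-month segment count only. Section 1.5 states that "The primary efficacy endpoint is the sensitivity and accuracy of detection of patients with myocardial dysfunction using MyoStrain® compared to standard assessments", and Section 11's power figure does not cover that endpoint.

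**What to change.** Two changes of wording in Section 11 are required.

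1. Where the imaging features are introduced, replace the subject number of 102 by 40 evaluable, and say what evaluable means.
2. Replace the sentence on 102 patients by text such as:

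> With 40 evaluable patients (20 per arm), SD 6.25 and an unadjusted two-sided 5% t-test as a planning approximation, power to detect a difference of 4 segments at 6 months (16.8 versus 12.8) is about 50%. Power of 90% is reached only for a difference of about 6.6 segments, and the expected 95% CI half-width is about 4.0 segments. Power is lower if fewer than 20 per arm have 6-month data. These figures apply to the 6-month segment count, not to the sensitivity and accuracy endpoint in Section 1.5.

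The cost is a less favourable power statement. No patients, data or analyses are added.

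Two further steps are optional and do not correct an error. The first is to use the root-mean-square SD of 6.44 (power 48%, 90% detectable difference 6.8, half-width 4.1). The second is to adjust the 6-month comparison for the baseline count of segments above −17%, already measured for entry under Section 5.1. No power gain should be claimed for this without a documented correlation.
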